7.6 Assessment of Expectedness

All SARs (SAEs determined as having a reasonable suspected causal relationship to fludrocortisone or midodrine) must be assessed for expectedness.

The assessment of expectedness will be performed by the CI, or delegated to a senior co-investigator in their absence, using the MHRA-approved RSI for the trial (see Section 6.2).

In the event of a SAR, which is thought to have occurred due to a reaction of another medicinal product with the IMP, please also ensure to check Section 4.5 'interaction with other medicinal products and other forms of interaction', of the SmPC detailed in Section 7.8 to assess relatedness. All AEs, and SAEs, unless exempt from reporting (see Section 7.3 and 7.7), occurring from point of randomisation to end of study participation must be recorded in the eCRF as well as the participant's medical notes.

7.7 Protocol Specific SAE Reporting Exclusions

Due to the large amount of comorbid disease, very high levels of illness and Adverse Events that we expect to be present in this population, the following SAEs will be recorded on the AE log within the eCRF, but not reported immediately to NCTU, and not reported using the SAE form:

- Any death or hospitalisation due to new cardiovascular event
- Any death or hospitalisation due to new diagnosis or treatment of cancer
- Any death or hospitalisation due to fall or fracture
- Any death or hospitalisation due to infection
- Any death or hospitalisation due to delirium
- Any hospitalisation due to reduced mobility
- Any death or hospitalisation due to exacerbation of an existing medical condition
- Any admission for elective or planned investigation or treatment
- Any hospitalisation due to nausea, vomiting, constipation or diarrhoea
- Any falls related soft tissue injury, which require medical attention

- Note that the above exceptions to immediate SAE reporting refer only to SAEs where the study medication is not deemed to be causally related to the event by the local PI. Where study medication is deemed to be causally related (SAR or SUSAR) by the local PI, immediate reporting of the event should proceed to NCTU using the CONFORM-OH SAE form.

7.9 Recording and Reporting SUSARs

All SUSARs or suspected SUSARs that occur during this study must be reported by site to the NCTU immediately (and no later than 24 hours of the site becoming aware of the event), through the provided SAE reporting method (see Section 7.5). This will automatically be distributed to the Sponsor and CI.

The assessment of expectedness will be performed by the CI, (or a medically qualified individual delegated this task via the Delegation Log, in their absence) against the approved RSI for the trial. The RSI is contained within Section 4.8 of SmPC:

- Fludrocortisone acetate 0.1 mg tablets
- Bramox 2.5 mg tablets*

* For the purpose of this study all midodrine brands will be referenced against the SmPC for Bramox 2.5 mg tablets.

All SUSARs must be reported to the MHRA and REC. Reporting to MHRA and REC will be performed by the study Sponsor. This is reported using the electronic SUSAR form via the eSUSAR website. A copy of the electronic form and the CTIMP safety report will be sent to the REC in line with Sponsor SOPs.

SUSARs which are determined as fatal and life-threatening must be sent to the MHRA within seven calendar days of notification (with a further eight days for follow-up information) by the Sponsor.

Non-life threatening SUSARs must be reported to the MHRA by the Sponsor no later than 15 calendar days with any relevant follow-up information sought and reported as soon as possible after the initial report.

NCTU will be responsible for ensuring that the CI reviews the expectedness assessment to determine if a SAR is unexpected and requires reporting as a SUSAR. The reporting timeframe starts at day zero when the Sponsor is in receipt of a minimum set of information:

- Sponsor trial reference and trial name (sponsor reference)
- EudraCT number
- Patient trial number and date of birth
- Name of IMP(s)
- Date of notification of the event
- Medical description of the event
- Date and time of the onset of the event (including event end date if applicable)
- Causality assessment
- Seriousness of the event, particularly if life threatening or fatal
- An identifiable reporter (e.g. Principal Investigator)

Sites must report the SUSAR/suspected SUSAR using the CONFORM-OH SAE Reporting Form. This form should be emailed to the trial SAE email address: [contact] (from a NHS.NET email account) which will then be automatically distributed to the trial management team, CI and nominated Sponsor contact. For sites that do not have nhs.net accounts, another secure method may be used but this must be discussed with and agreed by the NCTU Trial Manager(s) prior to use.

The site is expected to co-operate fully with NCTU and Sponsor staff, to ensure that a full and detailed report is submitted to the MHRA and REC within the required timelines.

Site PIs will be informed of all SUSARs reported for the study by NCTU.

7.10 Responsibilities

7.10.1 Principal Investigator

- Checking for AEs and ARs when participants attend for treatment or follow-up
- Using medical judgement in assigning seriousness and causality and providing an opinion on expectedness of events using the RSI version approved for the trial.
- Ensuring that all SAEs and SARs, including SUSARs, are recorded and reported to the Sponsor within 24 hours of becoming aware of the event and provide further follow-up information as soon as available.
- Ensuring that AEs and ARs are recorded and reported to the Sponsor in line with the requirements of the protocol.

7.10.2 Chief Investigator

- Clinical oversight of the safety of trial participants, including an ongoing review of the risk/benefit.
- Using medical judgement in assigning seriousness, causality and expectedness of SAEs where it has not been possible to obtain local medical assessment.
- Using medical judgement in assigning expectedness to SARs in line with the RSI.
- Immediate review of all SUSARs.
- Review of specific SAEs and SARs in accordance with the trial risk assessment and protocol.

- Review/assignment of Medical Dictionary for Regulatory Activities (MedDRA) or body system coding for all SAEs and SARs.
- Preparing the clinical sections and final sign off of the Development Safety Update Report (DSUR).

7.10.3 Sponsor

- Data collection and verification of AEs, ARs, SAEs, SARs and SUSARs onto a database (delegated to NCTU).
- Reporting safety information to the independent oversight committees for the ongoing assessment of the risk/benefit ratio throughout the life of the trial (delegated to NCTU).
- Assessment of expectedness of any SUSARs (delegated to the CI).
- Expedited reporting of SUSARs to the Competent Authority (CA) and REC within required timelines.
- Notification of all investigator sites of any SUSAR that occurs (may be delegated to NCTU).
- Reviewing RSI at least annually and notification of PIs of any required updates (delegated to NCTU).
- Preparing tables and other relevant information for the DSUR in collaboration with the CI and ensuring timely submission to the MHRA and REC (delegated to NCTU).

7.10.4 DMC

- Review of safety data collected to date to identify any trends.
- Make recommendations to the TSC on study conduct based on any findings from review of safety data.

7.10.5 TSC

- Act on recommendations from the DMC in relation to any safety issues identified in the TSC charter.

7.11 Notification of Deaths

Fatal SUSARs will be reported within seven days to Sponsor, REC and MHRA. Monitoring of all other deaths will occur via the TMG and the DMC.

7.12 Contraception and Pregnancy

The effect of midodrine on pregnancy has not been investigated in humans therefore the advice in the SmPC is that it is not recommended during pregnancy and in women of childbearing potential not using contraception. The SmPC for fludrocortisone indicates risks to the foetus when taken during pregnancy.

Pregnancy, lack of agreement by females to use effective contraception and lactation are all exclusion criteria and the PIL will advise females to contact the local trial team immediately should they become pregnant during the trial.

Highly effective methods of contraception include:

- combined (oestrogen and progestogen containing) hormonal contraception associated with inhibition of ovulation (oral, intravaginal, transdermal)
- progestogen only hormonal contraception associated with inhibition of ovulation (oral, injectable, implantable)
- intrauterine device (IUD)

- intrauterine hormone-releasing system (IUS)
- vasectomised partner (provided that partner is the sole sexual partner of the trial participant and that the vasectomised partner has received medical assessment of the surgical success)
- bilateral tubal occlusion
- sexual abstinence (defined as refraining from heterosexual intercourse during the entire period of risk associated with the study treatments. The reliability of sexual abstinence needs to be evaluated in relation to the duration of the clinical trial and the preferred and usual lifestyle of the subject).

7.13 Pregnancy Reporting

In the event of a study participant becoming pregnant during the study, the site must use a study-specific pregnancy reporting form to notify NCTU, the Chief Investigator and the Sponsor Representative within 24 hours of becoming aware of the pregnancy.

If a participant becomes pregnant, sites should follow routine practice. The participant should be completely withdrawn from the study and referred to the relevant team. Sites should approach the study participant to obtain consent to record the outcome of the pregnancy.

Pregnancy does not constitute a SAE but study participants that become pregnant must be followed up until at least the culmination of the pregnancy to determine if a congenital anomaly or birth defect has occurred. Only congenital anomalies or birth defects are reported as an SAE.

7.14 Overdose

Research teams should consult the SmPC for advice on the management of overdose.

In the event of reported minor overdose (three times usual dose), participants will be assessed by the research team by telephone, at home, GP surgery or local research unit, whichever is the more convenient. They will be given verbal instructions when seen by the research nurse to contact him/her should this occur. If clinically stable, they will be asked to stay at home for that day and avoid any further doses that day. If the participant is unwell, has taken a larger overdose or significant hypertension has been noted as a consequence of the overdose, the RN will refer them to their GP or else directly to A&E for admission and monitoring.

7.15 Reporting Urgent Safety Measures

An Urgent Safety Measure (USM) is an action that the Sponsor or an Investigator may take in order to protect the subjects of a trial against any immediate hazard to their health or safety. Upon implementation of an USM by an Investigator, the NCTU must be notified immediately and details of the USM given. The Sponsor must inform the MHRA and the NHS REC within three days of the USM taking place in accordance with the Sponsor's SOPs.

7.16 Development Safety Update Report (DSUR)

In the UK, a DSUR will be submitted to the MHRA and NHS REC once a year on the anniversary of the Clinical Trial Authorisation date. NCTU must ensure that the report is submitted within 60 days of the end of the reporting period. The Trial Management Group must contribute to the compilation of the DSUR and the CI must review and authorise the final report before it is ready for submission. The DSUR

should also be reviewed by the NCTU QA Manager and Sponsor Representative prior to submission. NCTU staff will prepare and submit DSURs for the trial, in accordance with NCTU SOPs.

8 STATISTICAL CONSIDERATIONS

8.1 Analysis Populations

The following analysis populations will be defined:

Analysis population	Definition
Efficacy Analysis Population 1 - Intention-to-treat (ITT)	
 Participants will be analysed according to their randomised treatment group, i.e. following the ITT principle All available outcome data will be included in the analysis
Efficacy Analysis Population 2	
 Participants will be analysed according to their randomised treatment group Outcome data following cross-over to another treatment group, or discontinuation of allocated treatment, will be set to missing
Safety population	
 For each treatment group, all participants exposed will be included in the safety population Safety data will be summarised according to the treatment strategy received at the time of onset of each AE

The primary outcome will be analysed in the intention-to-treat population with sensitivity analyses in the per-protocol population. Secondary outcomes will be analysed in the intention-to-treat population. Safety data will be reported in the safety population.

8.2 Statistical Analyses

The analysis will follow a fully detailed pre-specified SAP that is approved by the trial oversight committees. This SAP will be finalised prior to the first DMC review of unblinded data.

8.2.1 Analysis of the Primary Outcome Measure

The primary analysis will be a linear mixed-effects model fitted to OHQ at three and six months after baseline. Fixed effects will include treatment assignment, baseline OHQ, baseline age (≥ 80 or < 80 years) and aetiology (neurogenic vs non-neurogenic). A separate treatment assignment parameter will be included for each follow-up time. Random effects will include site and individual (as nested within site). From this model we will use the Wald test of each level of treatment assignment against control (reference) to test the null hypothesis of no treatment difference at six months. Confidence intervals and p-values can be extracted from this model directly. This model accounts for outcome data being missing under a missing at random assumption. We would not anticipate missing baseline data so will not use multiple imputation.

A pre-specified exploratory analysis will compare the clinical effectiveness of fludrocortisone with midodrine. This will use the same model as for the primary analysis.

8.2.2 Analysis of Secondary Outcome Measures

For secondary questionnaire and blood pressure outcomes we will use the same analysis as for the OHQ, except with the relevant baseline variable as a fixed effect instead of OHQ. For count variables (number of falls, number of fallers, number of syncopal events, number of hospitalisations) over 12 months we will use a negative binomial regression to allow for zero-inflation. This will be adjusted for age, aetiology and site. For time until first fall, a Cox regression model will be fitted adjusted for the same variables. Adverse Events will be tabulated by arm by type and severity.

8.2.3 Subgroup Analyses

For the primary outcome we will explore subgroup effects through including an interaction parameter in the primary analysis model described above. Variables we will consider are:

- Neurogenic OH and non-neurogenic OH
- Age ≥ 80 years versus age < 80 years
- Male versus female
- Presence of diabetes versus no diabetes

8.2.4 Interim Analyses and Criteria for the Premature Termination of the Trial

An interim analysis will be conducted after 200 participants have been randomised. Prior to this, an interim statistical analysis plan will be developed that fully specifies the statistical methods to be used. Briefly, a linear mixed-effects model will be fitted to three- and six-month OHQ data, with fixed effects for baseline OHQ data, treatment assignment and random effects for individual. This model will be used to estimate the difference in six-month OHQ between fludrocortisone and control and between midodrine and control. If the estimated difference for an experimental arm is 0 or less (corresponding to the arm having worse outcome than control), it will be recommended to be dropped from the trial. This recommendation will be ratified by the TSC and the DMC.

If one experimental arm is recommended for dropping at the interim analysis and this is ratified by the DMC, the trial will continue to its planned enrolment, but subsequent participants will be randomised 1:1 between control and the remaining experimental arm.

If both experimental arms are recommended for dropping at the interim analysis and this is ratified by the DMC, the trial will be terminated early.

8.3 Sample Size Calculation

The trial is testing two null hypotheses: 1) the mean difference in six-month OHQ between fludrocortisone and control is ≤ 0 ; and 2) the mean difference in six-month OHQ between midodrine and control is ≤ 0 .

With testing of each hypothesis at a two-sided 5% Type 1 error rate a three-arm trial without interim analyses would require $n=309$ participants with six month information, randomised 1:1:1 between the three arms, for 90% power. This assumes a standard deviation of 2.2 and minimally clinical informative difference (MCID) of 1.0 as found from the OHQ validation study [6] and confirmed by our PPI work.

The multi-arm design will control the total chance of falsely recommending an ineffective treatment (one-sided family-wise error rate, FWER) at 4.5%. With the possibility of early lack-of-benefit stopping, the FWER will be lower than this.

Assuming attrition of 15% (based on comparable clinical trials in older people of similar duration [33-37]) the recruitment target is 366 (122 per arm).

Taking into account the interim analysis, assuming that participants are recruited over a 30-month period with a staggered opening of sites, the power of the design to recommend each treatment is displayed in the table below (as determined from one million simulation replicates per scenario). This assumes only participants with six month data collected are included in the interim analysis. In practice including participants with three-month data but not yet six-month data will allow modest additional efficiency.

Scenario	Probability recommend fludrocortisone	Probability recommend midodrine	Probability recommend both	Probability recommend at least one
Mean effect of both = 0 (null scenario)	2.4%	2.4%	0.4%	4.4%
Fludrocortisone has MCID, midodrine effect = 0	91.8%	2.5%	2.5%	91.8%
Midodrine has MCID, fludrocortisone effect = 0	2.4%	91.7%	2.4%	91.7%
Both treatments have MCID effect	89.9%	89.7%	82.8%	96.8%

9. HEALTH ECONOMICS ANALYSIS

The study will include a within trial cost-utility analysis with longer-term model based extrapolation. For both the within trial analysis and the model based analysis the results will be reported as incremental costs, QALYs and incremental cost per QALY gained.

9.1 Within-trial Analysis of Costs and Outcomes

The within trial analysis cost and outcomes for the three trial intervention arms will be based on data collected over the 12-month follow-up period. Costs will be those that fall on the NHS, personal social services (PSS), participants and their families and will be based upon use of health and social services and, as part of the costs falling on patients and their families, the time and travel costs of accessing services. Costs will also be collected at baseline for the use of primary care services for the three months prior to baseline solely to allow costs to be adjusted for any baseline imbalances in the use of services.

The use of secondary services will be collected via an eCRF. Use of primary health care and personal social services will be collected by self-administered Health and Social Service Use questionnaires at baseline, three, six, and twelve months. Costs to participants and their families for private health care

and time away from usual activities will also be collected via the questionnaire noted above. The cost of secondary care will be based on standard sources e.g. NHS reference costs, BNF. Standard sources will also be used to cost care provided in primary or social care. These unit costs will be combined with the use of services data to estimate costs for each participant.

The costs of accessing care by participants and their families will be based on responses to a time and travel questionnaire completed at six months. The focus of this questionnaire is on the time and monetary cost incurred the last time a specific type of health care was used (e.g. general practice visit or an outpatient visit). The responses to this questionnaire will be used to estimate the unit costs to the participant and their family of accessing each type of care. Travel costs will be based on costs reported by participants and also on data routine sources (e.g. mileage costs). The time costs will be valued according to the type of activity that accessing care is displacing (work or leisure time) and valued appropriately based on a review of the literature in the UK. These unit costs will then be combined with the use of services data to estimate costs of time and travel cost for each participant.

From the costs estimated at three, six, and twelve months for each participant estimates a mean cost to the NHS and PSS, participant and their families and overall in each arm of the trial for the 12-month follow-up period will be calculated.

Health status, measured using the EQ-5D-5L will be collected from participants at baseline, three, six and 12 months. A proxy version of EQ-5D-5L will be included to be used for participants who are unable to self-complete the questionnaire. With the proxy version, the caregiver is asked to rate how he/she thinks the patient would rate his/her own health-related quality of life, if the patient were able to communicate.

The response to the EQ-5D-5L will be converted into scores using population tariffs [38]. These will then be converted into QALYs for each participant using the area under the curve approach. From the QALYs estimated for each participant, the mean QALYs for each arm of the trial for the 12-month follow-up period will be estimated.

Using the data on total costs per participant regression techniques will be used to identify any difference between fludrocortisone or midodrine compared to usual care when controlling for (base line factors as outlined in the statistical analysis and for costs the cost of primary care in the three months prior to randomisation). A similar approach will be used to estimate the difference in QALYs between the treatment strategies.

The cost and QALY regressions will be run simultaneously using seemingly unrelated regression (SUR)[39]. SUR permits the simultaneous estimation of costs and effects, calculated at individual level, while accounting for unobserved individual characteristics that could affect both costs and QALYs and lead to potential correlation between these two dependent variables [40].

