 - Standing nadir BP and postural BP drop will be measured from Lying Standing Blood Pressure (LSBP) collected at baseline, three, six and 12 months. Where follow-up is carried out face-to-face this will be measured according to local practice. If the participant is unable to attend a face-to-face visit (clinic or home visit) and follow-up is conducted remotely, either a postural BP assessment documented in the medical records (in the preceding eight weeks for the eligibility assessment, or the preceding six weeks for the follow-up timepoints), or a self-assessed LSBP may be used. Missing LSBP values and reasons will be closely monitored.
 - To allow for future changes to clinical services (e.g. temporary closure due to COVID-19), an automatic BP monitor will be provided to appropriate participants, alongside an instruction leaflet, to allow them to measure their own LSBP without the need for a hospital visit
 - Other important clinical outcomes including hospital admissions, Adverse Events and Adverse Reactions will be collected over the 12-month study period and recorded on the CRF and reported as per protocol.

Economics

- Use of health services over the 12-month follow-up period estimated from the Health and Social Service Use questionnaire collected at baseline (to control for baseline imbalances in use of health services), three, six and 12 months and from the CRF.

The Health and Social Service Use questionnaire is developed specifically to address the research questions posed in this study. It is informed by the Client Service Receipt Inventory (CSRI), [27] existing health service utilisation questionnaires collated by the MRC funded Database of Instruments for Resource Use Measurement (DIRUM) project (www.dirum.org).

The Health and Social Service Use questionnaire does not include medications, as the cost of common medication other than the trial medications will be negligible.

- Costs to the NHS, personal social services and patients over 12-month follow-up period estimated from responses to the Health and Social Service Use questionnaire (see above), the time and travel questionnaire completed at six months and from the CRF.

The Time and Travel questionnaire is developed specifically to address the research questions posed in this study. It is informed by the work of the UK working party on assessing patient costs and resources use questionnaires [28, 29] collated by the MRC funded DIRUM project.

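### The cost regression's only baseline cost term is primary-care cost, although social-services and private-care use are also collected at baseline and belong to the cost outcome

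*Protocol*

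**What the plan says.** Outcome. Protocol 9.1 defines the costs to be analysed: "Costs will be those that fall on the NHS, personal social services (PSS), participants and their families". The regression is run on total cost per participant, jointly with QALYs by seemingly unrelated regression (SUR).

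Covariates. The regression controls for "base line factors as outlined in the statistical analysis". Its one baseline cost term is given as "for costs the cost of primary care in the three months prior to randomisation". The first group can be read from Protocol 8.2.1: "Fixed effects will include treatment assignment, baseline OHQ, baseline age" group and aetiology, with site as a random effect.

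Baseline data. Protocol 9.1 states: "Use of primary health care and personal social services will be collected by self-administered Health and Social Service Use questionnaires at baseline, three, six" (its list of visits ends at 12 months). Protocol 3.4.2 adds private care to the services recorded at baseline, and the schedule in Protocol 5.5 places the questionnaire at the baseline visit. Yet the baseline costing sentence in 9.1 covers one component: "Costs will also be collected at baseline for the use of primary care services for the three months prior to baseline solely" for adjustment.

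Purpose. Protocol 3.4.2 describes the questionnaire as "collected at baseline (to control for baseline imbalances in use of health services", and says later that the pre-randomisation data serve only to adjust for imbalance in resource use.

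**The concern.** If adjustment is the only reason given for collecting baseline use, the adjustment model would be expected to use what was collected. As 9.1 stands, the baseline PSS and private-care items have no stated role in the analysis.

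Nothing else in the design stands in for them. Minimisation (Protocol 5.3) uses age group, aetiology and centre. The remaining covariates are baseline OHQ, age group and aetiology. None of these measures earlier use of social care. If by chance one arm starts with more social-care users, part of that difference passes into its 12-month cost.

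The quantity affected is the incremental cost, which is the numerator of the cost per QALY. What is at stake is its precision and its accuracy given the baseline imbalance that actually occurred.

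**Working it through.** **Arm size.** The point rests on no figure stated in the plan; the planned arm size is used only to size chance imbalance. It reproduces. A two-sample t-test for a difference of 1.0 with SD 2.2, two-sided 5% and 90% power needs 102.7, so 103 per arm (309 in all). With 15% attrition, 103 / 0.85 = 121.2, so 122 per arm and 366 in all.

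**Inputs not in the documents.** No cost SD, PSS share of cost, or baseline-to-follow-up correlation is given. Two quantities are assumed:
- s, the share of PSS in the total-cost variance left after the planned adjustment: 0.10 to 0.75
- ρ, the correlation of baseline with follow-up PSS cost: 0.3 to 0.7

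Baseline PSS cost is taken to be unrelated to the other covariates and to the other cost components.

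**Precision.** Adding baseline PSS cost as a covariate gives partial R² = s × ρ², an SE ratio of √(1 − sρ²), and a gain in effective sample size of 1/(1 − sρ²) − 1.

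| s | ρ | sρ² | SE ratio | SE reduction | Effective n |
|---|---|---|---|---|---|
| 0.10 | 0.3 | 0.009 | 0.995 | 0.5% | +0.9% |
| 0.25 | 0.5 | 0.0625 | 0.968 | 3.2% | +6.7% |
| 0.50 | 0.5 | 0.125 | 0.935 | 6.5% | +14.3% |
| 0.50 | 0.7 | 0.245 | 0.869 | 13.1% | +32.5% |
| 0.75 | 0.7 | 0.3675 | 0.795 | 20.5% | +58.1% |

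These figures are for PSS cost with its own coefficient. A single summed baseline cost forces one slope on primary care and PSS, so its gain can be smaller.

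**Chance imbalance.** With n per arm, the difference in mean baseline PSS cost between two arms has SE √(2/n) baseline SDs.
- n = 122: √(2/122) = 0.128, so a 95% range of ±1.96 × 0.128 = ±0.25 SD.
- n = 10 (illustrative only): √(2/10) = 0.45 SD.

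The part carried into the incremental cost has SE √(sρ²) × √(2/n), in units of the total-cost residual SD. At 122 per arm this runs from √0.009 × 0.128 = 0.012 to √0.3675 × 0.128 = 0.078.

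**Bias.** A simulation of two arms of 122 (4,000 replicates, normal costs, primary-care cost already in the model) compared the estimate with and without the PSS term. In all three settings the mean estimate was within 0.004 SD of zero, the true difference, for both models. The ratio of the SD of the estimate with the term to that without it was 0.99 (s = 0.25, ρ = 0.3), 0.94 (s = 0.5, ρ = 0.5) and 0.84 (s = 0.5, ρ = 0.7). In the simulation s is the share of total variance before primary-care cost is removed, so these ratios need not equal the table's. The direction and rough size agree.

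**The case against.** The strongest objection is that section 9.1 is an outline and the operative document is elsewhere. SAP 1.2.2 leaves quality of life, QALYs, costs and cost-effectiveness to a Health Economics Analysis Plan, which was not supplied and may already name a wider covariate. This stands as a limit on confidence. It does not make the text of 9.1 consistent with 3.4.2.

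Second, the trial closed to recruitment nine months into the pilot (SAP 1.1), and the SAP plans no statistical testing (SAP 3.3). Those statements govern the clinical analyses, but nothing supplied shows that the cost regression will still be run. This lowers the practical weight. It does not remove the point, because the SAP, written after closure, still assigns the cost objectives to the economics plan, and chance imbalance is larger in small arms.

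Third, the choice of prognostic covariates is partly the analyst's preference, and under randomisation the standard error already reflects chance imbalance. That is right as far as validity goes. The loss is in efficiency and in accuracy given the observed imbalance.

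Four stronger readings are tempting, and the documents do not support them:
- A reader might infer that primary-care cost is the only adjustment. The same sentence of 9.1 also brings in the baseline factors of the statistical analysis; primary care is the only baseline **cost** term.
- A reader might infer that the incremental cost is biased. Allocation is randomised, and the simulation shows no bias with or without the term.
- A reader might infer that baseline PSS cost is ready to use. Baseline **use** is collected; 9.1 describes baseline costing for primary care alone.
- A reader might assume that baseline PSS cost has a partial correlation of 0.3 to 0.7 with total cost, so that the SE falls by 1 − √(1 − 0.09) = 5% to 1 − √(1 − 0.49) = 29%. Total cost also contains secondary care, primary care, private care, time and travel. At 0.7, three months of one component would explain about half of all residual variance, and a floor of 5% hides the negligible cases.

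**Conclusion.** The point holds as an inconsistency within the protocol with a modest statistical cost. The cost model in 9.1 uses less baseline information than the trial collects, and less than the purpose stated in 3.4.2 implies. The estimate stays unbiased over repeated randomisation, loses some precision, and is not corrected for chance imbalance in PSS use.

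On the assumptions above, the avoidable part of the standard error runs from about 0.5% to about 20%. The documents cannot narrow this range, and its lower end is negligible. Severity is low: the operative economics plan is unseen, and after early closure the point matters only if the cost regression is carried out.

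**What to change.** Reconcile 9.1 with 3.4.2. In 9.1 and in the Health Economics Analysis Plan, replace the primary-care covariate with one summed three-month baseline cost of all questionnaire-measured services within the perspective analysed:
- NHS and PSS perspective: primary care plus PSS
- where participant costs are counted: private care added

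Enter this term in the cost equation only; SUR allows the two equations to have different covariates. A single sum replaces one covariate with another, so it adds no parameter. That suits a small sample better than separate component terms.

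The cost is a line of text in each document and no new data collection. Baseline PSS and private-care use would have to be costed, with the same unit costs as at follow-up. The plan should also confirm that those items use the three-month look-back that 3.4.2 gives for health services. The documents do not clearly say that secondary-care use before randomisation is collected, so that component would remain unadjusted, and the text should say so.

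If no cost regression is run, reporting baseline PSS use by arm would let readers judge the imbalance for themselves.
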